10.2.2 Day 1 visit

- Complete physical exam
- For women of child bearing potential: blood pregnancy test

10.2.3 Semiannual visits

Semiannual visits will be performed at 6 month intervals (+/-14 days) in reference to the Day 1 visit.

10.2.3.1 Clinical assessments

- Complete physical exam.
- IMP compliance.
- AE
- Concomitant medications
- SF-36

10.2.3.2 Laboratory tests

- CBC (includes red blood cell count, hemoglobin, hematocrit, mean corpuscular volume, mean corpuscular hemoglobin, mean corpuscular hemoglobin concentration, reticulocyte count, white blood cell count and differential, platelet count).
- Biomarkers: serum chitotriosidase; plasma MIP1- β ; serum P1NP; serum CTX that must be collected after overnight fasting; plasma GL-1; plasma lyso-GL-1.
- For women of child bearing potential: blood pregnancy test

10.2.3.3 Special provision for URM patients

CYP2D6 URM patients will have liver and spleen MRI and hematology performed every 6 month till week 52. However, the frequency of liver and spleen MRI and hematology can be increased to every 3 month till week 52 at the discretion of the Investigator. After week 52 CYP2D6 URMs patients will follow the standard schedule.

10.2.4 Annual visits

Annual visits will be performed once a year (+/-14 days) in reference to the Day 1 visit.

In addition to the assessments of the semiannual visits the following assessments will be performed.

10.2.4.1 Clinical assessments

- Gaucher assessments

10.2.4.2 Imaging

- DXA of both hips and the lumbar spine
- MRI of entire bilateral femur and lumbar spine

- Liver and spleen MRI
- At the 2nd and 4th anniversaries only, X-Ray of femur and lumbar spine.

10.2.5 Study completion or patient discontinuation/withdrawal

10.2.5.1 Clinical assessments

- Complete physical exam including weight
- Gaucher disease clinical assessments
- SF-36
- IMP compliance.
- AE
- Concomitant medications

10.2.5.2 Laboratory assessments

- CBC
- Biomarkers

10.2.5.3 Imaging

- X-Ray femur and spine, unless it was performed less than 2 years prior
- DXA hip and spine, unless it was performed less than 1 year prior
- Bone MRI, unless it was performed less than 1 year prior
- Liver and spleen MRI, unless it was performed less than 1 year prior

10.3 DEFINITION OF SOURCE DATA

Source Data are defined as original documents, data and records. This includes but is not limited to hospital records, clinic and office charts, study-specific source document worksheets, phone logs, memoranda, evaluation checklists, laboratory requisitions and reports, MRI, DXA, X-Ray reports, local laboratory reports, medication dispensing reports and any other documents regarding the patient.

10.4 HANDLING OF PATIENT TEMPORARY OR PERMANENT TREATMENT DISCONTINUATION AND OF PATIENT STUDY DISCONTINUATION

The IMP should be continued whenever possible. In case the IMP is discontinued, it should be determined whether the discontinuation can be made temporarily; permanent IMP discontinuation should be a last resort. Any IMP discontinuation should be fully documented in the patient's

medical file and the IMP Accountability CRF. In any case, the patient should remain in the study as long as possible.

10.4.1 Temporary treatment discontinuation with investigational medicinal product(s)

Temporary treatment discontinuation may be considered by the Investigator because of suspected AEs. Reinitiating of treatment with the IMP will be done under close and appropriate clinical/and or laboratory monitoring once the Investigator will have considered according to his/her best medical judgment that the responsibility of the IMP(s) in the occurrence of the concerned event was unlikely and if the selection criteria for the study are still met, and after discussion with Genzyme (refer to [Section 7.1](#) and [7.2](#)).

For all temporary treatment discontinuations, duration should be recorded by the Investigator in the IMP administration CRF.

If a patient becomes pregnant during her participation in the study she may remain in the study, but must suspend the IMP till delivery and while breast feeding. The maximum duration of such an IMP suspension is 12 months. During the IMP suspension the patient must maintain compliance with all the other study requirements, except for the radiological examinations that are prohibited in pregnant women.

10.4.2 Permanent treatment discontinuation with investigational medicinal product(s)

Permanent treatment discontinuation is any treatment discontinuation associated with the definitive decision from the Investigator or the patient not to re-expose the patient to the IMP during the duration of the study.

10.4.3 Criteria for permanent treatment discontinuation

The patients may withdraw from treatment with the IMP if they decide to do so, at any time and irrespective of the reason, or this may be the Investigator's decision. All efforts should be made to document the reasons for treatment discontinuation and this should be documented in the e-CRF.

The use of eliglustat is prohibited in combination with Class IA and Class III antiarrhythmic medications. See [Section 8.5.1.1](#) for detail.

Patients requiring medications incompatible with eliglustat because of drug-drug interaction for longer than 2 weeks should be discontinued from the study. See [Section 8.5.1.2](#) for detail.
Handling of patients after permanent treatment discontinuation

Patients will be followed-up according to the study procedures as specified in this protocol up to the scheduled date of study completion, or up to recovery or stabilization of any AE to be followed-up, whichever comes last, unless the patient is lost to follow up.

If possible, and after the permanent discontinuation of treatment, the patients will be assessed using the procedure normally planned for the last visit at study completion or patient discontinuation/withdrawal.

All cases of permanent treatment discontinuation should be recorded by the Investigator in the appropriate pages of the CRF when considered as confirmed.

10.4.4 Procedure and consequence for patient withdrawal from study.

The patients may withdraw from the study before study completion if they decide to do so, at any time and irrespective of the reason.

If possible, the patients are assessed using the procedure normally planned for the visit at study completion or patient discontinuation/withdrawal.

For patients who fail to return to the site, the Investigator should make the best effort to recontact the patient, and to determine his/her health status, including at least his/her vital status. Attempts to contact such patients must be documented in the patient's records (eg, times and dates of attempted telephone contact, receipt for sending a registered letter).

The statistical analysis plan will specify how these patients lost to follow-up for their primary endpoints will be considered.

Patients who have withdrawn from the study cannot be enrolled again in the study. Their inclusion and treatment numbers must not be reused.

10.5 OBLIGATION OF THE INVESTIGATOR REGARDING SAFETY REPORTING

10.5.1 Definitions of adverse events

10.5.1.1 Adverse event

An **adverse event** (AE) is any untoward medical occurrence in a patient or clinical investigation patient administered a pharmaceutical product and which does not necessarily have to have a causal relationship with this treatment.

10.5.1.2 Serious adverse event

A **serious adverse event** (SAE) is any untoward medical occurrence that at any dose:

- Results in death, or
- Is life-threatening, or
 - Note: The term "life-threatening" in the definition of "serious" refers to an event in which the patient was at risk of death at the time of the event; it does not refer to an event which hypothetically might have caused death if it were more severe.
- Requires inpatient hospitalization or prolongation of existing hospitalization, or
- Results in persistent or significant disability/incapacity, or
- Is a congenital anomaly/birth defect

- Is a medically important event

Medical and scientific judgment should be exercised in deciding whether expedited reporting is appropriate in other situations, such as important medical events that may not be immediately life-threatening or result in death or hospitalization but may jeopardize the patient or may require medical or surgical intervention (ie, specific measures or corrective treatment) to prevent one of the other outcomes listed in the definition above.

Note: The following list of medically important events is intended to serve as a guideline for determining which condition has to be considered as a medically important event. The list is not intended to be exhaustive nor indicative of expected AEs:

- Any reason for intensive treatment in an emergency room or at home
- Cancers diagnosed during the study or aggravated during the study (only if judged unusual/significant by the Investigators in oncology studies)
- Chronic neurodegenerative diseases (newly diagnosed) or aggravated during the study (only if judged unusual/significant by the Investigators in studies assessing specifically the effect of a study drug on these diseases).

10.5.1.3 Adverse event of special interest

An adverse event of special interest (AESI) is an AE (serious or non-serious) of scientific and medical concern specific to Genzyme product or program, for which ongoing monitoring and immediate notification by the Investigator to Genzyme is required. Such events may require further investigation in order to characterize and understand them. Adverse events of special interest may be added or removed during a study by protocol amendment.

For this study the following AEs will be considered as AESI and should be reported as such to GPE:

- Clinically significant cardiac arrhythmias detected by ECG or Holter monitoring that do not meet criteria for an SAE.
- Syncope from any cause.
- Pregnancy of a female patient as well as pregnancy occurring in a female partner of a male patient.
- Pregnancy will be qualified as an SAE only if it fulfills one of the seriousness criteria (see Section 10.5.1.2).

In the event of pregnancy in a female patient, IMP should be suspended. See [Section 10.4.3](#) for detail.

Female patients will be instructed to notify the investigator immediately if they discover they are pregnant. Pregnant female patients will be discontinued from the study.

Male patients will be instructed to notify the investigator immediately if they discover that their sexual partner is pregnant.

If the investigator learns of a report of pregnancy at any time after signing the informed consent, the investigator should follow the instructions in [Section 10.5.4](#) to contact the sponsor within 24 hours; however, the investigator will be asked to complete the Pregnancy forms rather than SAE forms. The patient will be followed until the outcome of the pregnancy is known (eg, live birth or stillbirth). The investigator will be responsible for this follow-up.

Follow-up of the pregnancy in a female patient or in a female partner of a male patient is mandatory until the pregnancy outcome has been determined, unless prohibited by local regulations.

- Symptomatic overdose (serious or non-serious) with IMP
 - A symptomatic overdose (accidental or intentional) with the IMP is an event suspected by the Investigator or spontaneously notified by the patient (not based on systematic pills count) and defined as administration of a quantity of IMP per administration or per day, which is above the maximum recommended dose according to the authorized product information

If overdose is suspected, the patient will be asked to suspend the IMP immediately and come back to the site for appropriate monitoring.

Asymptomatic overdose has to be reported as a standard AE.

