7.3 PATIENT DISCONTINUATION/WITHDRAWAL CRITERIA

Patients are free to discontinue participation or withdraw consent from the study at any time, for any reason, and without prejudice to further treatment. Patients who discontinue/withdraw from this study will receive treatment as deemed appropriate by their treating physician.

A patient's participation in the study also may be discontinued at any time at the discretion of the Investigator or Sanofi Genzyme. The Investigator will contact Sanofi Genzyme Clinical Study Director if a patient meets any of the withdrawal criteria. The following may be justifiable reasons for the Investigator or Sanofi Genzyme to remove a patient from the study:

- The patient was erroneously included in the study.
- The patient is uncooperative, including failure to appear at one or more study visits, or is not compliant with taking study medication.
- The patient develops an exclusion criterion or concurrent disease.
- The patient receives other investigational product(s) during the course of this study.
- The patient experiences an AE that is considered intolerable by the patient or investigator.
- Sanofi Genzyme terminates the study.
- If a female patient of childbearing potential has a positive pregnancy test blood β -hCG or is lactating after first dosing with eliglustat in this study, the patient may remain in the study, but must suspend eliglustat till delivery and while breast feeding. The maximum duration of such an IMP suspension is 12 months. During the IMP suspension the patient must maintain compliance with all the other study requirements, except for the radiological examinations that are prohibited in pregnant women.

If a patient meets at least 1 of the following criteria, the Investigator must notify the Sanofi Genzyme Clinical Study Director. The Investigator and Sanofi Genzyme will review the clinical status of the patient and will determine if the patient should be withdrawn from the study.

- The patient's hemoglobin level falls below 80 g/L and remains below 80 g/L when the test is repeated within approximately 2 weeks.
- The patient's platelet count falls below 50×10^9 /L and remains below 50×10^9 /L when the test is repeated within approximately 2 weeks,
- The patient experiences a clinically significant bleeding episode assessed by the Investigator as related to a low platelet count.

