8.1.2 IMP temporary suspension

Treatment with eliglustat should be suspended in patients who require short-term treatment with

- A strong or moderate CYP2D6 inhibitor with a strong or moderate CYP3A inhibitor in CYP2D6 EMs and IMs.
- A strong or moderate CYP3A inhibitor in CYP2D6 PMs.

These medications can be used for up to 2 weeks at a time.

All IMP temporary suspension should be documented in the IMP distribution CRF.

Up to 2 episodes of eliglustat suspension are allowed per year.

If these medications are required for longer treatment periods, the investigator should consult with the Clinical Study Director.

If a patient becomes pregnant during her participation in the study she may remain in the study, but must suspend eliglustat until delivery and while breast feeding. The maximum duration of such an IMP suspension is 12 months. During the IMP suspension the patient must maintain compliance with all the other study requirements, except for the radiological examinations that are prohibited in pregnant women.

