- After obtaining the necessary signed informed consent from the pregnant female partner directly, the Investigator will record pregnancy information on the appropriate form and submit it to the Sponsor within 24 hours of learning of the partner's pregnancy. The female partner will also be followed to determine the outcome of the pregnancy. Information on the status of the mother and child will be forwarded to the Sponsor. Generally, the follow-up will be no longer than 6 to 8 weeks following the estimated delivery date. Any termination of the pregnancy will be reported regardless of fetal status (presence or absence of anomalies) or indication for procedure.

Female participants who become pregnant

- The Investigator will collect pregnancy information on any female participant who becomes pregnant while participating in this study. Information will be recorded on the appropriate form and submitted to the Sponsor within 24 hours of learning of a participant's pregnancy. The participant will be followed to determine the outcome of the pregnancy. The Investigator will collect follow-up information on the participant and the neonate, and the information will be forwarded to the Sponsor. Generally, follow-up will not be required for longer than 6 to 8 weeks beyond the estimated delivery date. Any termination of pregnancy will be reported, regardless of fetal status (presence or absence of anomalies) or indication for procedure.
- Any pregnancy complication or elective termination of a pregnancy will be reported as an AE or SAE. A spontaneous abortion is always considered to be an SAE and will be reported as such. While the Investigator is not obligated to actively seek this information in former study participants, he or she may learn of an SAE through spontaneous reporting.
- Any female participant who becomes pregnant while participating in the study must stop study treatment as soon as a pregnancy is confirmed and will be either withdrawn from the study or remain in the study. If a pregnant patient decides to remain in the study she must suspend the IMP till delivery and while breast feeding. The maximum duration of such an IMP suspension is 12 months. During the IMP suspension the patient must maintain compliance with all the other study requirements, except for the radiological examinations that are prohibited during pregnancy.

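### Protocol 10.5.1.3 removes every pregnant patient from the study, four other passages let her stay with drug suspended, and its cross-reference leads to the wrong section

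*Protocol*

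**What the plan says.** Five places in the protocol say what happens when a patient becomes pregnant during the study.

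- **Section 10.5.1.3 (adverse events of special interest).** On drug: "In the event of pregnancy in a female patient, IMP should be suspended", with a pointer to Section 10.4.3 for detail. On study participation: "Pregnant female patients will be discontinued from the study". On follow-up: "The patient will be followed until the outcome of the pregnancy is known".
- **Section 7.3 (discontinuation/withdrawal criteria).** "the patient may remain in the study, but must suspend eliglustat till delivery and while breast feeding".
- **Section 8.1.2 (temporary suspension).** "If a patient becomes pregnant during her participation in the study she may remain in the study", again with eliglustat suspended.
- **Section 10.4.1 (temporary treatment discontinuation).** "she may remain in the study, but must suspend the IMP till delivery and while breast feeding".
- **Appendix A.** The patient stops treatment and "will be either withdrawn from the study or remain in the study"; if she decides to remain, the same suspension terms apply.

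The last four all cap the suspension at 12 months and keep the other study requirements in force, apart from radiological examinations prohibited in pregnancy.

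Section 10.4.3, the target of the pointer, is titled "Criteria for permanent treatment discontinuation". It covers patient or investigator decisions, antiarrhythmics and incompatible medications needed for more than 2 weeks. It does not mention pregnancy.

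**The concern.** A rule that removes every pregnant patient cannot stand beside passages that let her stay. The conflict sits where it will be used: Table 2 in Section 10.5.4 sends anyone reporting a pregnancy to 10.5.1.3, and SAP Section 2.1.4.1 takes its definition of adverse events of special interest from the same section.

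The choice has consequences for the data. Section 7.3 uses discontinuation and withdrawal together, and Section 10.4.4 bars withdrawn patients from enrolling again. If a patient discontinued under 10.5.1.3 is handled as withdrawn, the step cannot be reversed. She would not resume drug in the study or have scheduled bone imaging after delivery. Patients who leave are not replaced (Section 7.3) and missing values are not imputed (Section 11.4). Disposition counts and recorded exposure would also differ between the two readings.

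**Working it through.** **1. The passages side by side**

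| Protocol place | Drug | Study participation |
|---|---|---|
| 10.5.1.3 | Suspended | Discontinued, no exception |
| 7.3 | Suspended, up to 12 months | May remain |
| 8.1.2 | Suspended, up to 12 months | May remain |
| 10.4.1 | Suspended, up to 12 months | May remain |
| Appendix A | Stopped; suspended up to 12 months if she remains | Withdrawn or remains |

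The drug column agrees on stopping drug during pregnancy. The participation column does not: one entry is mandatory removal and four allow her to stay.

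Reading discontinued as merely off drug does not resolve this. The sentence says from the study, and 10.5.1.3 has already dealt with drug separately. The protocol also keeps the two ideas apart elsewhere: under 10.4.3 and 10.5.2, patients who stop drug are still observed to the end of the study. Section 10.5.1.3 is also in tension with itself, since suspending drug implies possible resumption and leaving the study does not.

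**2. The cross-reference**

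10.5.1.3 points to 10.4.3, which has no pregnancy text. The suspension paragraph is in 10.4.1.

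**3. Weight of one patient**

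1/32 = 3.1%, using the approximate sample size in Section 11.1.

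**4. Which two-year scans depend on the rule**

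Inputs: annual MRI and DXA, and X-ray at the 2nd and 4th anniversaries (10.2.4.2); visits within ±14 days of schedule (10.2.4); no imaging with a positive pregnancy test (10.1). *Assumption, not in the documents:* a pregnancy lasts 266 to 280 days, depending on how its start is dated, and reaches term.

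Latest start day that still allows a scan on the last day of the window = last window day − pregnancy length.

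- Week 52: Day 364 + 14 = 378. 378 − 280 = 98; 378 − 266 = 112.
- Week 104: Day 728 + 14 = 742. 742 − 280 = 462; 742 − 266 = 476.

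| Pregnancy starts | If she remains | If she is discontinued |
|---|---|---|
| By about Day 98–112 | Week 52 and Week 104 MRI and DXA possible | Neither |
| After that, by about Day 462–476 | Week 104 MRI, DXA and X-ray possible | None |
| Later, before the Week 104 imaging | Week 104 imaging may be missed | Week 104 imaging may be missed |
| After the Week 104 imaging | Two-year imaging unaffected | Two-year imaging unaffected |

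Start days up to the Week 104 cutoff are 462/728 = 63.5% to 476/728 = 65.4% of the two-year period. This is a share of days, not a pregnancy risk.

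**5. Sensitivity to the SAP windows**

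SAP Table 2 assigns MRI and DXA to wider windows than the visit schedule (Schedule B: Week 52 to Day 545, Week 104 to Day 909). With those limits:

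- Week 52: 545 − 280 = 265; 545 − 266 = 279.
- Week 104: 909 − 280 = 629; 909 − 266 = 643, or 629/728 = 86.4% to 643/728 = 88.3% of days.

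Late scans would therefore widen the gap between the two rules. They enter the two-year analysis only if collected before the data cut in SAP Section 3.

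**The case against.** The textual contradiction and the wrong cross-reference are not in dispute. The case against giving them weight is as follows.

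- **The effect may be nil.** Every version stops drug, pregnancy outcome is followed in any case, contraception or abstinence is an entry condition, and all analyses are descriptive. This stands, and it limits the size of the point. It does not remove the conflict between two operative instructions.
- **The ±14-day windows are not the ones used in analysis.** This is correct. The cutoffs in step 4 describe scheduled scans only, and step 5 shows that the SAP windows move them later, which increases the difference between the rules.
- **The four permissive passages are not identical.** The text in 7.3 sits in a list of reasons for removing a patient, Appendix A makes remaining the patient's decision, and 8.1.2 and 10.4.1 do not say who decides. This is fair and worth settling in the same edit, but all four allow her to stay.
- **Removal need not end imaging.** The discontinuation visit includes MRI and DXA unless done less than 1 year before (10.2.5.3), and no date is fixed for it. A scan after delivery is therefore not strictly excluded. With imaging barred while the test is positive, her last bone images would ordinarily predate the pregnancy. If no annual visit had taken place, they would be the screening images or accepted prior-study images up to 1 year old (10.2.1.2).
- **Retained scans may follow up to a year off drug.** This is true, and exposure duration is counted regardless of unplanned intermittent discontinuations (protocol 11.4.1, SAP 2.4.3.1). It bears on how such data are read, not on whether the passages agree.

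**Conclusion.** The concern holds on both parts: the protocol contradicts itself on whether a pregnant patient stays in the study, and the pointer in 10.5.1.3 leads to a section with no relevant text. It should be corrected.

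The numerical effect is small and uncertain. Each affected patient is about 3% of roughly 32, and the documents do not say how many could be affected. For a pregnancy starting by about Day 462–476, scheduled Week 104 bone imaging is possible under one reading and lost under the other. That rests on the assumed 266–280 days to term, the ±14-day visit window, and discontinued being handled as leaving the study without imaging after delivery. The irreversibility rests on discontinued also being treated as withdrawn under 10.4.4.

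**What to change.** Reconcile Section 10.5.1.3 with Sections 7.3, 8.1.2, 10.4.1 and Appendix A so that one rule, chosen by the sponsor, applies throughout, and say who makes the decision if there is one to make. This review takes no position on which rule is right. Change the cross-reference in 10.5.1.3 from 10.4.3 to 10.4.1, where the pregnancy text now sits.

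The cost is one sentence and one cross-reference in 10.5.1.3, or matching wording in the other four passages if the sponsor chooses that rule. No new data are needed, and the reconciliation itself needs no SAP change: the suspension passages are already in the protocol, and the SAP already defines exposure regardless of intermittent discontinuations.
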